## 10. Statistical Considerations

### 10.1. Sample Size Determination

Approximately 708 patients will be randomized in order that 600 patients complete the study through the primary endpoint at Week 26.

Patients will be randomized in a 2:2:1 ratio to double-blind LY900014 dosed 0 to 2 minutes before meals, double-blind Humalog dosed 0 to 2 minutes before meals, or open-label LY900014 dosed up to 20 minutes after the start of a meal. Stratification will be by country, HbA1c stratum ( $\leq 8.0\%$ ,  $> 8.0\%$ ), type of basal insulin (insulin glargine, insulin detemir, or insulin degludec), and age group (1 to  $< 12$  years, 12 to  $< 18$  years).

Assuming a NIM of 0.4%, no true difference between treatment groups and an SD of 1.1%, 240 completers for each double-blind treatment group will provide greater than 95% power to show noninferiority between LY900014 and Humalog using the upper limit of a 2-sided 95% CI (LY900014–Humalog). This sample size also has more than 80% power to show noninferiority between LY900014 and Humalog using a 0.3% NIM at 26 weeks.

With the assumption a difference no larger than 0.07% between treatment groups and a SD of 1.1%, 240 completers of double-blind Humalog dosed 0 to 2 minutes before meals and 120 completers of open-label LY900014 dosed up to 20 minutes after the start of a meal will provide approximately 76% power to show noninferiority between open-label LY900014+20 and double-blind Humalog using a NIM of 0.4%.

Assuming a 15% dropout rate during 26 weeks of treatment, approximately 708 patients (283 patients in each double-blind treatment group and 142 patients in the open-label treatment group) will need to be randomized.

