Efficacy analyses will be conducted on all randomized patients according to the treatment the patients are assigned. The analyses for the primary and gated objectives will be performed for the efficacy estimand including data collected prior to permanent discontinuation of investigational product (IP) and for the intention-to-treat (ITT) estimand including all data collected regardless of IP use. The primary endpoint will also be analyzed using the Per Protocol (PP) and Completer populations.

Unless otherwise specified, the efficacy analyses for other secondary objectives and exploratory objectives will be performed for the efficacy estimand. When change from baseline is included as a response variable of analysis models, the patient will be included in the analysis only if a baseline and at least 1 postbaseline measurement are available, except for the analysis for ITT estimand on primary endpoint. The analysis for the ITT estimand will include all randomized patients with a baseline.

Safety analyses will be conducted on the Safety Population. Analyses of adverse events (AEs) will include 2 sets of analyses, unless otherwise specified. The first set of analyses will include data collected prior to permanent discontinuation of IP. The second set of analyses will include all data collected during the course of the entire study including the follow-up visit, regardless of IP use. Analyses of hypoglycemia will use data collected prior to permanent discontinuation of IP; while analyses for post-treatment may be performed as needed. Analyses of safety laboratory measurements will be performed on all data during the planned treatment period regardless of IP use.

The data on IP is defined based on the following rules:

- For data only measured at an office visit (for example, vital signs, safety laboratory tests, and questionnaires) will be considered as on IP if the measurement was performed at or prior to the cutoff date defined as 14 days after the last IP dose date
- For data collected as running records with an exact date stamp such as AEs and hypoglycemia events from patient diary where the dates of the measures were not tied with the date of an office visit, postbaseline data with dates \leq (last study drug dose date +1 day) will be considered as data on IP.
- For insulin dose data including both basal and prandial insulin dose, the dose used between the first IP dose date and the last IP dose date will be considered as data on IP.

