- For the 7-point self-monitored blood glucose (SMBG) profiles, the profiles measured after the first IP dose date and prior to the last IP dose date will be considered as data on IP.

Unless otherwise noted, all tests of treatment effects will be conducted at a 2-sided alpha level of 0.05, and confidence interval (CI) will be calculated at 95%, 2-sided. All tests of interactions between treatment groups and other factors will be conducted at a 2-sided alpha level of 0.05. Countries in similar geographic regions with fewer than 10 patients, based on all Randomized Population, will be pooled to achieve a pooled country of at least 10 patients. All analyses using country in the model will use a pooled country, unless otherwise specified. The final pooling by country and geographic region will be finalized prior to data lock.

[Table ITSB.5.2](#) shows the definition of baseline and post-baseline for each variable to be analyzed. The baseline variables are derived from the evaluable data during the baseline period.

Table ITSB.5.2. Baseline and Postbaseline Definitions and Patient Population by Study Period and Type of Analysis

Study Period/Analysis	Patient Population	Baseline Observations	Post-Baseline Observations
Lead-In Period			
HbA1c ANCOVA	All Randomized Patients	Visit 1	Visit 4 prior to initiation of IP
Basal, bolus, and total insulin doses, and bolus/total insulin dose ratios continuous analysis	All Randomized Patients	Not applicable	Visit 3-4
TEAE	All Enrolled Patients	Prior to first dose of open-label insulin lispro (or Visit 2 date if the dose date is missing)	The entire lead-in period after first dose of open-label insulin lispro and prior to the first dose of IP (or Visit 4 if the dose date is missing)
26-Week Treatment Period (including Safety Follow-Up Visit where applicable)			
HbA1c ANCOVA (ITT estimand)	All Randomized Patients	Last of Visits 1-4	Visit 15 with imputation for patients who discontinue study prior to Visit 15
HbA1c MMRM (efficacy estimand)	All Randomized Patients with a baseline and at least one post-baseline observation while on IP	Last of Visits 1-4	Visits 7, 10, and 15 prior to discontinuation of IP
HbA1c categorical analysis longitudinal logistic regression	All Randomized Patients with a baseline and at least one post-baseline observation while on IP	Last of Visits 1-4	Visits 7, 10, and 15 prior to discontinuation of IP

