5.11. Efficacy Analyses

5.11.1. Primary Outcome and Methodology

The primary objective of this study is to test the hypothesis that LY900014 is noninferior to Humalog on glycemic control (noninferiority margin [NIM]=0.4% for HbA1c) in patients 1 to <18 years of age with T1D, when administered as prandial insulin, in combination with basal insulin for 26 weeks. There will be 2 primary analysis methods, each tested at the full significance level of 0.05.

For the US FDA submission (using the ITT estimand), all randomized subjects, regardless of their postbaseline result availability, will be included in the analysis. Due to COVID-19, patients are allowed to have their laboratory data collected at a local laboratory if there is any ongoing extenuating situation, such as travel restriction. HbA1c data collected from the local laboratory will be included in the analysis in the same way as those collected from the central laboratory. The missing endpoints will be imputed by the copy reference or the return to baseline approach. For the copy reference approach, the reference for each treatment group is from the retrieved dropout patients who discontinue IP but have the measurement at the primary endpoint in the same treatment group. If there are only a limited number of patients in the reference group that leads to a failure in performing the proposed multiple imputation analysis such that the model cannot converge, or the number of records in the reference group is less than the number of records with missing data, the missing endpoints will be imputed by the return to baseline

approach. For the return to baseline approach, the patient-level observed baseline value plus a noise will be used to impute the missing endpoints. The noise follows a normal distribution with the variability estimated from the “washout HbA1c data.” The “washout HbA1c data” will be derived by subtracting the corresponding treatment mean at Week 26 from individual non-missing HbA1c values at Week 26. After imputation, the primary efficacy comparison will be based on the contrast between LY900014 and Humalog from an ANCOVA. The model for the change from baseline to the Week 26 HbA1c endpoint will include treatment and strata (pooled country, type of basal insulin, and age group) as fixed effects and baseline HbA1c as a covariate. The final estimates will be the combined estimates from at least 1000 imputations.

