For non-FDA submissions, the primary efficacy comparison will be based on the contrast between LY900014 and Humalog at Week 26 (Visit 15) from the MMRM analysis of change from baseline in HbA1c including data collected from all randomized patients prior to permanent discontinuation of IP through Week 26 (efficacy estimand). In contrast to the population of ITT estimand, randomized patients with a baseline and at least one postbaseline result will be included in the analysis. The model for the analysis of the primary efficacy endpoint of change from baseline in HbA1c will include the fixed class effects of treatment, strata (pooled country, type of basal insulin, and age group), visit, and treatment-by-visit interaction, as well as the continuous, fixed covariates of baseline value. An unstructured covariance structure will be used to model the within-patient errors. Significance tests will be based on LS means and Type III tests. If this analysis fails to converge, the following covariance structures will be tested in order:

- Toeplitz with heterogeneity
- autoregressive with heterogeneity
- compound symmetry with heterogeneous variances
- Toeplitz
- autoregressive
- compound symmetry without heterogeneous variances

The first covariance structure that converges will be used. The Kenward-Roger approximation will be used to estimate denominator degrees of freedom.

For both primary analysis approaches, LY900014 will be declared noninferior to Humalog if the upper limit of the 2-sided 95% CI for the LS mean difference in the change from baseline in HbA1c for LY900014 minus Humalog is below +0.4%. In addition, the 95% CI for the treatment difference will be compared to an alternative NIM of +0.3%. Both estimands will be tested at the full significance level of 0.05.

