5.11.3. Sensitivity Analyses for Missing Data

A missing-not-at-random-based analysis will be performed for both the efficacy and ITT estimands to assess sensitivity of departures from the missing-at-random (MAR) assumption. The tipping-point approach that will be used is similar to a progressive stress test (Ratitch et al. 2013). The basic idea is to impute the missing values and add a value (delta) to the imputed values of the experimental treatment group and perform an analysis for the primary endpoint on the delta-adjusted data set to see whether the conclusion of the primary analysis is overturned. If not, a larger delta is chosen and the process repeated until the primary result is overturned. If the delta required to overturn the primary result is not a plausible departure from MAR, then the primary result is robust to plausible departures from MAR. The initial delta is set to 0.1 with an increment of 0.1. Imputation under the noninferiority null method (where delta equals the NIM=0.4) will be included as a special case of the progressive stress test.

For the ITT estimand, the imputation of missing data will be as described for the FDA primary analysis, and ANCOVA on the change from baseline to Week 26 in HbA1c will be used.

For the efficacy estimand, the copy reference approach will be used to impute missing data and the reference group will be the Humalog treatment group. Imputation will be for all longitudinal visits.

Sensitivity Analyses for Missing Data due to COVID-19 pandemic:

Missing data due to the pandemic represents an extraordinary circumstance, and missing data could be more prevalent in some geographic regions than in others. Lilly has been following a mitigation plan that aims to reduce the impact from the pandemic. Nevertheless, Lilly expects missing data at the primary endpoint visit, Visit 15 HbA1c, for COVID-19 related reasons:

- COVID-19 infection (adverse event) or death caused by infection,
- Discontinuation of treatment due to COVID-19 related reasons,
- Discontinuation of study due to COVID-19 related reasons, and
- Completed the 26 week treatment period, but missed primary endpoint due to COVID-19 related reasons.

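### The efficacy-estimand tipping-point analysis by default omits patients with no on-drug post-baseline HbA1c, so its tipping delta is biased upward for the randomized population

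*SAP*

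**What the plan says.** SAP 5.1 sets a general rule for models of change from baseline. A patient enters "only if a baseline and at least 1 postbaseline measurement are available, except for the analysis for ITT estimand on primary endpoint". The next sentence there opens the ITT analysis to every randomized patient with a baseline.

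The efficacy estimand follows the rule. The MMRM row of Table ITSB.5.2 defines its population as "All Randomized Patients with a baseline and at least one post-baseline observation while on IP" and lists Visits 7, 10 and 15. SAP 5.11.1 draws an explicit contrast with the ITT population: "randomized patients with a baseline and at least one postbaseline result will be included in the analysis".

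SAP 5.11.3 then describes a progressive stress test for both estimands. Missing values are imputed, a delta is added in the experimental arm, and delta rises in steps of 0.1 until the primary conclusion is overturned. Delta = 0.4 is included as a special case. For the efficacy estimand, imputation is by copy reference from Humalog, and "Imputation will be for all longitudinal visits". That sentence names visits. No sentence in 5.11.3 names the patients for this estimand or sets the rule in 5.1 aside.

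**The concern.** A patient with a baseline and nothing afterwards adds no information to the MMRM, so leaving such patients out of the primary model is harmless. A stress test works differently, because delta acts only through the patients whose values are imputed. If some patients with missing data are removed first, the same delta moves the LY900014 mean less, and a larger delta is needed to overturn noninferiority.

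SAP 5.11.3 judges robustness by asking whether the overturning delta is plausible, so an inflated delta makes the result look sturdier than it is for the randomized population. The estimand concerned is the primary one for non-FDA submissions and, under Protocol 10.3.3.1, for publications.

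**Working it through.** **Inputs.** Noninferiority requires that the upper 95% confidence limit for the difference in change in "HbA1c for LY900014 minus Humalog is below +0.4" (per cent). Protocol 10.1 assumes no true difference, an SD of 1.1, 240 completers and 283 randomized per blinded arm, and 15% dropout. It gives no dropout timing.

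**1. The plan's own figures.** SE = 1.1 × √(2/240) = 0.1004. Power = Φ(0.4/0.1004 − 1.96) = Φ(2.02) = 97.8%, which agrees with "240 completers for each double-blind treatment group will provide greater than 95% power to show noninferiority". For dropout, 240/0.85 = 282.4, rounded up to 283. Patients without a Week 26 value: 283 − 240 = 43 per arm, or 43/283 = 15.2%.

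**2. Who is left out.** The first post-baseline HbA1c is at Visit 7, Week 6 ± 7 days. SAP 5.1 counts an office-visit value as on IP up to 14 days after the last dose. A patient seen exactly at Week 6 therefore needs a last dose at Week 4 or later (Week 3 to Week 5 across the visit window). The group is roughly those who stop before about Week 4, and smaller if an early-discontinuation HbA1c is mapped to a visit.

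**3. Tipping delta.** Let e be the number per arm with no on-IP post-baseline HbA1c (an assumption), and d the observed difference. With these patients excluded, the imputed share of the LY900014 arm is

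p = (43 − e)/(283 − e),

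and the upper limit is approximately

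U(Δ) = d + Δp + 1.96 × √[1.1² × (2/240) + Δ²p(1 − p)/(283 − e)].

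The tipping delta is the smallest Δ with U(Δ) ≥ 0.4. Including every patient corresponds to e = 0. Two cases with d = 0:

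- e = 0: p = 0.152. At Δ = 1.29, U = 0.196 + 1.96 × √(0.01008 + 0.00076) = 0.196 + 0.204 = 0.400.
- e = 10: p = 33/273 = 0.121. At Δ = 1.60, U = 0.193 + 1.96 × √(0.01008 + 0.00100) = 0.193 + 0.206 = 0.400 after rounding.

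| Excluded per arm (e) | Imputed share p | Tipping delta, d = 0 | Increase |
|---|---|---|---|
| 0 | 15.2% | 1.29 | 0% |
| 5 | 13.7% | 1.43 | 11% |
| 10 | 12.1% | 1.60 | 24% |
| 15 | 10.4% | 1.84 | 42% |

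Increases come from unrounded values. For orientation only, if the 43 stopped evenly over 26 weeks, 43 × 4/26 = 6.6 per arm would stop before Week 4. The relative effect barely depends on d: for e = 10 the delta goes from 1.90 to 2.34 at d = −0.1, from 0.86 to 1.07 at d = +0.07, and from 0.67 to 0.83 at d = +0.1.

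**4. The prespecified case Δ = 0.4.** The shift in the LY900014 mean is 0.4 × 0.152 = 0.061 with everyone included and 0.4 × 0.121 = 0.048 with ten excluded. The largest observed difference that still passes is 0.4 − 0.061 − 0.1975 = 0.142 in the first case and 0.4 − 0.048 − 0.197 = 0.154 (rounded) in the second. Only a result between these two values would change this case.

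**5. Simulation check.** This used 60 simulated trials per case, no true difference, assumed between-visit correlations of 0.5 to 0.7, copy-reference imputation from Humalog and delta steps of 0.1. The median tipping delta rose from 1.40 to 1.50 with five excluded and from 1.45 to 1.65 with ten. The delta under exclusion was at least as large in 97% and 100% of trials respectively.

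**The case against.** **The ITT stress test covers these patients.** A reader might infer that the earliest dropouts are stress-tested nowhere. The documents do not support that. The ITT tipping point uses the FDA primary imputation, which takes in all randomized patients whatever their post-baseline data, so an early LY900014 dropout with a missing Week 26 HbA1c is imputed and receives delta. Two things remain. It tests a different estimand with a different imputation. And a patient who stops IP early but returns for the Week 26 HbA1c, as Protocol 8.1 encourages, is observed under ITT and receives no delta there either.

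**The exclusion is inferred.** SAP 5.11.3 states no analysis set for this estimand. SAP 5.1 makes the Randomized Population the default for efficacy analyses unless otherwise stated, and imputing every visit could be read to include baseline-only patients. But 5.1 does state otherwise: it sets a specific rule with one named exception, and this analysis is not it. If inclusion was always intended, the fix only records it.

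**The group may be very small.** The 14-day window narrows it, and the Schedule of Activities has an HbA1c at the early-discontinuation visit. This stands in part. Under Protocol 8.1, patients who stay in the study off IP have no early-termination procedures. Table ITSB.5.2 lists only Visits 7, 10 and 15 for this model, although its continuous safety-laboratory row does mention early-discontinuation visits.

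**The consequence is modest.** This stands. At d = 0 the delta with everyone included, 1.29, is already more than three times the margin. Where plausibility would be argued harder, as at d = +0.1, excluding five patients moves the delta from 0.67 to 0.74, less than one grid step.

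**Conclusion.** The point holds within the efficacy estimand. Under the SAP's default rule, patients with no on-IP post-baseline HbA1c drop out of the tipping-point analysis before imputation. If the LY900014 arm has any, the tipping delta is biased upward as a measure for all randomized patients.

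The direction is firm. The size rests on a count that the documents do not give: 0%, 11%, 24% or 42% for 0, 5, 10 or 15 excluded per arm, assuming 283 per arm, 43 missing at Week 26, equal exclusions in both arms, an SD of 1.1 and an observed difference of 0.

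Two stronger readings should be resisted. One is that the noninferiority conclusion itself is in doubt: the primary MMRM is unaffected. The other is that early dropouts are where missing-at-random is least credible, or that they make up a large share of all dropouts: the documents give neither reasons for nor timing of early discontinuation. This is a cheap improvement to a supportive analysis.

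**What to change.** In SAP 5.1, extend the exception so that it also covers the efficacy-estimand missing-data sensitivity analyses of 5.11.3, which would then include all randomized patients with a baseline. In 5.11.3, state that:

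- Visits 7, 10 and 15 are imputed for patients with no on-IP post-baseline HbA1c;
- delta is added to those imputed values in the experimental group, as for other missing values;
- the number of such patients is reported by arm beside the tipping delta.

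The population of the primary MMRM stays as it is. The cost is a few sentences of SAP text and a small programming change, with no new data. The one downside for the sponsor is a somewhat less favourable tipping delta if such patients exist.

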5.2. Adjustments for Covariates

Stratification factors of this study include country, HbA1c stratum ($\leq 8.0\%$, $>8.0\%$), type of basal insulin at randomization (insulin glargine, detemir or degludec), and age group (1 to <12, 12 to <18 years). Stratification factors will be entered into the interactive web-response system (IWRS) for randomization and also collected in the database by electronic case report form (eCRF) or central laboratory. The analysis models will use the stratification factors as collected in the database.

For the primary analysis of HbA1c, the stratification factor of HbA1c stratum will not be included. Instead, the continuous value of baseline HbA1c will be included in the analysis models.

Other efficacy analyses will include the stratification factors as noted in Sections 5.11 and 5.12.

5.3. Handling of Dropouts or Missing Data

The analysis for the primary and gated objectives will be performed for the ITT estimand including all data collected through Week 26 regardless of IP use and the efficacy estimand including data collected prior to permanent discontinuation of IP through Week 26.

For the US Food and Drug Administration (FDA) submission, the ITT estimand will be used. For the analysis of HbA1c, imputation of missing data will be performed as described in Section 5.11.1.

For non-FDA submissions, the efficacy estimand will be used. The missing data will be addressed by using a mixed-effect model repeated measures (MMRM) analysis. The MMRM model provides consistent estimator when data are missing at random. The model implicitly adjusts for missing data through a variance-covariance structure. An ANCOVA model will also

be used in the analysis of HbA1c. Unless otherwise stated, missing endpoints will be imputed using the last-observation carried forward (LOCF) approach, using only postbaseline data.

5.4. Multicenter Studies

Countries in similar geographic regions with fewer than 10 patients, based on the Randomized Population, will be pooled to achieve a pooled country of at least 10 patients. All analyses using country in the model will use a pooled country, unless otherwise specified. The final pooling by country and geographic region will be finalized prior to data lock.

